#### **Local Cutaneous Reactions at the Injection Site**

Local cutaneous reaction at injection site (LCRIS) is defined as (A) moderate or severe Injection Site Erythema, Swelling, Pruritus, Pain or Tenderness that started on the day of injection, persisted for at least two days; or (B) any AE at the injection site, regardless of severity, that leads to discontinuation of study drug, where AE at the injection site is the principal reason for discontinuation.

Percentage of injections leading to local cutaneous reaction at the injection site will be calculated as follows for each subject:  $(A/B)*100$ , where A=number of injections with a LCRIS, and B=total number of injections. Doses that are split across multiple injections are counted as a single injection.

Local cutaneous reactions at the injection site will be listed by preferred term.

### Flu-like Reactions

Flu-like reactions will also be summarized by preferred term.

Flu-like reactions are defined as either (A) flu-like illness or (B) pyrexia or feeling hot or body temperature increased, plus at least two of the following: Chills, Myalgia, and Arthralgia, starting on day of injection or the next day.

Percentage of injections leading to flu-like reactions will be summarized using the descriptive statistics.

Percentage of the injections leading to flu-like reactions will be calculated as follows for each subject:  $(A/B) \times 100$ , where A=number of injections leading to flu-like reactions, and B=total number of injections.

Flu-like reactions will be listed by preferred term.

### AE of special interest (AESI): Platelet reduction

Per protocol, severe reductions in platelet count  $< 50,000/\text{mm}^3$  accompanied by a major bleeding (MB) event or clinically-relevant non-major bleeding (CRNMB) event, or platelet count of  $< 25,000/\text{mm}^3$  independent of a MB or CRNMB event are considered as AESI. The AEs meeting the AESI criteria will be captured in the AE CRF page with a check box to indicate. AESI will be summarized by preferred term. A listing of AESI will also be provided.

### 3.7.3 Laboratory Measurements

Chemistry including thyroid panel and inflammatory, hematology, coagulation, complement, and urinalysis (result, change and percent change from baseline) will be summarized by treatment group and each post-baseline visit. All ALT, AST, and Platelet data from both the central and local laboratories will be summarized. For the rest of the parameters, only the central laboratory values will be summarized. For urinalysis, only P/C ratio, Protein, and Urine Creatinine will be tabulated.

For ALT and AST, the number and percent of subjects falling in each of the following categories will be tabulated by treatment group:

- ALT/AST  $> 3 \times \text{ULN}$ , confirmed
- ALT/AST  $> 5 \times \text{ULN}$ , confirmed

A confirmed value is based on a consecutive lab value performed on a different day to, but within 7 days of, the initial value. If that value is in the same or worse category, then the initial value is confirmed. If the consecutive value is in a better category, then the initial value is confirmed using the consecutive value category. If there is no retest within 7 days, then the initial value is presumed confirmed.

If there are multiple results on the same day (no matter from the same lab vendor or different lab vendors), then the worst value will be utilized in the analysis.

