#### **1.2.4. Safety Endpoint**

Incidence and severity of treatment-emergent adverse events (TEAE) (including hypotension and orthostatic hypotension), use of concomitant medications, abnormal findings in laboratory assessments, electrocardiogram (ECG), and vital signs

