### 8.5. Safety Monitoring Rules

Please refer also to the ‘Guidance for Investigator’ section of the Investigator’s Brochure.

For the purposes of the renal and platelet safety monitoring rules, Baseline is defined as:

- The last non-missing measurement prior to the first dose

In addition to the standard monitoring of clinical safety parameters, the following guidelines are provided for the monitoring of selected parameters chosen based on preclinical and clinical observations.

Confirmation Guidance: At any time during the study (Treatment or Post-Treatment Periods), the initial clinical laboratory results meeting the safety monitoring criteria presented below **must be confirmed** by performing measurements (ideally in the same laboratory that performed the initial measurement) on new specimens. All new specimen collections should take place as soon as possible (ideally within 3 days of the initial collection). For stopping rules, if the initial laboratory result is observed during the Treatment Period, the results from the retest **must be available** prior to administering the next dose of Study Drug (ISIS 757456 or placebo).

Re-dosing Guidance: Subjects with initial laboratory test values that reach a stopping rule must not be re-dosed until the re-test results are available. In general, subjects who do not meet the stopping rules based upon retest may continue dosing. However, the Investigator and the Sponsor Medical Monitor (or appropriately qualified designee) should confer as to whether additional close monitoring of the subject is appropriate. If any of the stopping criteria described below (refer to Section 8.6.1 to Section 8.6.5) are met, the subject will be permanently discontinued from further treatment with Study Drug (ISIS 757456 or placebo), evaluated fully as outlined below and in consultation with the Sponsor Medical Monitor or appropriately qualified designee, and will be followed up in accordance with Section 8.8 of the protocol.

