### **9.3. Definitions**

#### **9.3.1. Adverse Event**

An AE can be any unfavorable and unintended sign (including an abnormal laboratory finding, for example), symptom, or disease temporally associated with the use of medicinal (investigational) product, whether or not the AE is considered related to the medicinal (investigational) product.

An AE can therefore be any of the following:

- Any unfavorable and unintended sign (including an abnormal laboratory finding), symptom, or disease temporally associated with the use of a medicinal product, whether or not considered related to the medicinal product
- Any new disease or exacerbation of an existing disease (a worsening in the character, frequency, or severity of a known condition)
- Recurrence of an intermittent medical condition (e.g., headache) not present at Baseline
- Any deterioration in a laboratory value or other clinical test (e.g., ECG, X-ray) that is associated with symptoms or leads to a change in study treatment or concomitant treatment or discontinuation from Study Drug

AEs that are related to a protocol-mandated intervention, including those that occur prior to assignment of study treatment (e.g., screening invasive procedures such as biopsies).

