## **9.5. Procedures for Handling Special Situations**

### **9.5.1. Abnormalities of Laboratory Tests**

Clinically significant abnormal laboratory test results may, in the opinion of the Investigator, constitute or be associated with an AE. Examples of these include abnormal laboratory results that are associated with symptoms, or require treatment, e.g., bleeding due to thrombocytopenia, tetany due to hypocalcemia, or cardiac arrhythmias due to hyperkalemia. Whenever possible, the underlying diagnosis should be listed as AEs rather than as abnormal laboratory values.

Clinically significant abnormalities will be monitored by the Investigator until the parameter returns to its baseline value or until agreement is reached between the Investigator and Sponsor Medical Monitor. Laboratory abnormalities deemed not clinically significant by the Investigator should not be reported as AEs. Similarly, laboratory abnormalities reported as AEs by the Investigator should be deemed CS on the laboratory sheet.

The Investigator is responsible for reviewing and signing all laboratory reports. The signed clinical laboratory reports will serve as source documents and should include the Investigator's assessment of clinical significance of out of range/abnormal laboratory values.

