### **10.6.2. Safety Analysis**

The safety analysis will be conducted on the Safety Population.

Treatment duration and amount of Study Drug (ISIS 757456 or placebo) received will be summarized by treatment group. Subject incidence rates of all AEs will be tabulated by Medical Dictionary for Regulatory Activities (MedDRA™) system organ class, and by MedDRA™ term. Narratives of treatment emergent deaths, serious and AEs of special interest, including early withdrawals due to AEs, will also be provided.

All treatment emergent AEs, all treatment emergent AEs potentially related to Study Drug, all treatment emergent serious AEs, and all treatment emergent serious AEs potentially related to Study Drug (ISIS 757456 or placebo) will be summarized.

Laboratory tests to ensure subject safety including chemistry panel, complete blood count with differential, coagulation panel, complement etc., will be summarized by study visits for each treatment group. These safety variables will also be presented as change and percent change from Baseline over time after Study Drug (ISIS 757456 or placebo) administration, as appropriate.

Vital sign and ECG measures will be tabulated by treatment group. In addition, the number of subjects who experience abnormalities in clinical laboratory evaluations will be summarized by treatment group.

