#### Analytical visits

Data will be summarized using the visit labels provided in the data. Multiple results with the same visit label will be averaged. Results with visit labels as "Unscheduled" will not be included in the by-visit summary tables and figures except for determining baseline and the analysis of confirmed ALT/AST category (see section 3.7.3) but will be presented in data listings.

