### 3.7.2 Adverse Events

The incidence of adverse events (AEs) will be summarized by Medical Dictionary for Regulatory Activities (MedDRA) version 22.0 (or higher) preferred term and system organ class for:

- Any treatment emergent adverse events (TEAEs).
- Related TEAEs. Related is defined as "Related", "Possible", or missing relationship to study drug.
- Any TEAEs by severity. At each severity level of subject summarization, a subject is classified according to the highest severity if the subject reported one or more events. AEs with missing severity will be categorized as "Missing" for this summary.
- Serious TEAEs (Treatment-emergent SAEs).
- TEAEs leading to permanent study drug discontinuation.

Serious and non-serious AEs that lead to study discontinuation or investigational drug discontinuation will be listed separately. Non-treatment emergent adverse event will be included and be noted in the subject AE listing.

To determine the AE as treatment-emergent or not, if there is no "Formlink" link, and the AE (start date/time) occurs after the subject's first dosing date/time, then the AE is treatment-emergent. Otherwise, if the AE (start date/time) occurs prior to the subject's first dosing date/time, then the AE is not treatment-emergent.

In addition, if there is a "Formlink" link between two AE records, then we compare them pairwise, and consider two cases, where we compare the AE severity (mild/moderate/severe) and seriousness (Yes/No) between the two records in the pair. We chronologically order the 2 records (by AE start date) and refer to the "first" and "second" AE.

Case 1: The first AE record in the pair occurs before first dosing, and the second AE record occurs after first dosing.

If the AE severity or seriousness of the second record is worse than that of the first record, then only the second AE is deemed as a TEAE. Otherwise, neither record is considered as TEAE.

Case 2: Both AE records in the pair occur after first dosing.

If the AE severity or seriousness of the second record is worse than that of the first record, then two TEAEs are recorded. Otherwise only the first AE record is deemed as a TEAE.

All TEAEs identified based on the rules above will be summarized in the event number analysis.

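### Protocol 10.6.2 promises by-arm counts of subjects with laboratory abnormalities; SAP 3.7.3 specifies them only for confirmed ALT/AST, leaving abnormalities that never become adverse events uncounted

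*Combined protocol and SAP*

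**What the plan says.** Protocol 1.2.4 includes "abnormal findings in laboratory assessments" in the safety endpoint, and SAP 1.3.3 repeats it. Protocol 10.6.2 then plans two laboratory outputs. One is by-visit summaries with change from Baseline. The other, stated as an addition and without limit to any analyte, is that "the number of subjects who experience abnormalities in clinical laboratory evaluations will be summarized by treatment group".

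SAP 3.7.3 carries the by-visit summaries forward for all panels. Its only subject count is introduced by "For ALT and AST, the number and percent of subjects falling in each of the following categories will be tabulated by treatment group", and the two categories are confirmed ALT/AST above 3 and above 5 times ULN. Local laboratory results are summarized only for ALT, AST and platelets. Under the analytical-visits rule in SAP 3.2.1, results labelled as unscheduled "will not be included in the by-visit summary tables and figures except for determining baseline and the analysis of confirmed ALT/AST category".

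The contents list of the SAP shows no redacted entry within 3.7, whose subsections run from 3.7.1 to 3.7.6 without a gap.

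**The concern.** The SAP narrows a protocol commitment on a named safety endpoint and gives no reason. Safety versus placebo is a stated objective, and protocol 3.3 gives adequate assessment of safety as the basis for the sample size. Every subject takes an ACE inhibitor or an ARB, and protocol 2.2 names hyperkalemia and acute renal failure as complications of combined RAAS blockade. The protocol sets numerical renal, potassium and platelet limits, yet the SAP plans no by-arm count of subjects who cross them. For these analytes a by-arm count exists only through the adverse event tables, which depend on investigator judgement. A count taken from the values does not.

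**Working it through.** No figure in the plan needs reproducing. The check compares what is promised with what is specified, then asks what the adverse event tables recover.

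**1. Coverage of the laboratory count.** Protocol Appendix B lists 22 chemistry-panel analytes. SAP 3.7.3 counts subjects for ALT and AST: 2/22 = 9%, leaving 20. Hematology has 13 items if the three red-cell indices and five differential cell types are listed separately, and none is counted. No urinalysis result is counted.

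**2. What the by-visit tables omit.** Protocol 8.5 asks for a confirming specimen ideally within 3 days. Post-Baseline chemistry is scheduled on Days 8, 15, 22, 29, 36, 43, 50 (7 visits) and 57, 64, 78, 92, 120, 141 (6 visits), 13 in all. The shortest gap on nominal days is 7 days, so a retest within 3 days is an extra draw. If labelled unscheduled, it leaves the by-visit tables. If it carries the scheduled visit's label, SAP 3.2.1 averages it with the first value. Protocol 6.2 recommends a local draw for some repeat specimens early in dosing, creatinine included, and a local creatinine result is not summarized.

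**3. By-visit extremes do not give a subject count.** Assume 20 active subjects (30 × 2/3). Out-of-range minima at two visits may come from one subject or two:
- 1/20 = 5% (exact 95% CI 0.1 to 24.9%)
- 2/20 = 10% (exact 95% CI 1.2 to 31.7%)

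The intervals overlap almost entirely, so at this size the count is descriptive.

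**4. What the adverse event tables recover.** Protocol 9.3.1 makes a laboratory deterioration an adverse event when it is "associated with symptoms or leads to a change in study treatment or concomitant treatment or discontinuation from Study Drug". Hence:
- An 8.6.2 renal criterion met during dosing stops the drug, so it should appear in SAP 3.7.2 under "TEAEs leading to permanent study drug discontinuation".
- Confirmed potassium of 5.5 mmol/L or more during dosing holds the drug (8.5.4). At 6.0 or more, ACE/ARB treatment is to be stopped at any time in the study (8.6.4). Both are treatment changes.
- Platelets below 50,000/mm³ with major or clinically relevant bleeding, or below 25,000/mm³ regardless, are counted as events of special interest.
- Any other abnormality judged clinically significant and reported as an adverse event is counted through Day 141.

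**5. What remains.** Protocol 9.5.1 states: "Laboratory abnormalities deemed not clinically significant by the Investigator should not be reported as AEs". Two groups follow.
- Abnormalities below any action limit and judged not clinically significant. Platelets from the LLN down to 75,000/mm³ are an example: Table 6 continues dosing and assigns no special-interest status.
- An 8.6.2 crossing first met after the last dose, without symptoms or treatment and not judged clinically significant. No dose remains to be stopped. Of the 13 chemistry visits, 6 (46%) fall here, covering (141 − 50)/(141 − 1) = 91/140 = 65% of the time from first dose to last visit.

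**6. What is still undefined.** The limits exist in 8.5.4, 8.6.2, 8.6.4, Table 6 and the laboratory reference ranges. For non-liver tests, two things are missing: a confirmation window for analysis, and a rule for a value with no retest. Protocol 8.6.1 and SAP 3.7.3 settle these for ALT/AST only.

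**7. Why range flags or grades alone would not suffice.** From a creatinine of 0.80 mg/dL, 8.6.2 criterion 1 is met at max(0.80 + 0.30, 0.80 × 1.40) = 1.12 mg/dL (+0.32, +40%). The documents give no ULN. Over an assumed range, 1.12 is within normal and ungraded at a ULN of 1.2 or 1.3, and mild in Appendix D at 1.1. The renal criteria need their own rows.

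**The case against.** The strongest reply is that little of clinical weight is lost. Investigators must review every laboratory report for clinical significance, laboratory adverse events are graded by Appendix D, and SAP 3.7.2 tabulates them by severity and by discontinuation. Hyperkalemia at the action limits and on-treatment renal stops reach those tables. This stands, and it confines the gap to the remainder in step 5. The second group there also needs several conditions to coincide.

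It can also be said that the first, scheduled value stays in the by-visit table, that unscheduled results are listed, and that listings for about 30 subjects allow a hand count. That is true, but a hand count is not the planned by-arm summary that 10.6.2 promises.

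Finally, the SAP does not withdraw 10.6.2, and SAP 3.2.1 says in general terms that categorical data will be counted. That sentence defines no laboratory category, so a programmer following 3.7.3 exactly would produce only the ALT/AST table.

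**Conclusion.** The gap between protocol and SAP is real, and its consequence is descriptive. By-arm laboratory counts are specified for 2 of 22 chemistry analytes and for none in hematology or urinalysis. The uncounted remainder is abnormalities judged not clinically significant and symptom-free, untreated renal crossings after the last dose. This assumes that sites apply 9.3.1 and 9.5.1 as written and that 3.7.3 is complete as published.

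Three stronger readings are not supported.
- A reader might infer that the report will compare laboratory abnormalities by arm for the liver only. The adverse event and special-interest tables count many others.
- A reader might infer that any other count would be invented after seeing the data. The thresholds are already in the protocol; only the confirmation window and the no-retest rule are open. The count promised in 10.6.2 is of abnormalities, not confirmed ones, so in its basic form it needs neither.
- A reader might go through Appendix D and treat each row without a laboratory count as a missing table. Appendix D grades adverse events, and several rows, such as the phosphate disorders, hyperuricemia and hematuria, cannot be graded from a value alone.

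**What to change.** Add to SAP 3.7.3, on the Safety Set and by arm:
- the number and percent of subjects with any post-Baseline value outside the normal range, for each analyte;
- the number and percent meeting each protocol threshold: the 8.6.2 creatinine, eGFR and UPCR criteria; potassium ≥ 5.5 and ≥ 6.0 mmol/L; platelets below the LLN and in each Table 6 band.

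Use scheduled and unscheduled results, and judge local results against their own laboratory's reference range. State a confirmation window for the non-liver thresholds and say whether a value with no retest is presumed confirmed. Use Appendix D grades only where the value alone determines the grade.

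The cost is one or two extra descriptive tables from data already collected. No sample, visit or protocol change is needed, and the primary analysis and the operation of the stopping rules stay as they are.

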#### **3.7.4 Vital Signs**

Vital signs will include orthostatic assessment (supine and standing), heart rate, respiratory rate, body temperature, BMI and systolic and diastolic blood pressure. Except for systolic and diastolic blood pressure, which are pharmacodynamic endpoints for this study and will be summarized separately, other vital signs will be summarized by treatment group for vital sign values as well as the change and percent change from baseline at each post-baseline visit.

#### **3.7.5 12-Lead Electrocardiograms (ECG)**

Safety 12 lead ECG will be performed at the visits indicated in the protocol Schedule of Procedures.

The ECG data will include ventricular rate (VR), PR interval, QRS duration, QT, and corrected QT intervals, and overall interpretation.

For the continuous variables above, descriptive statistics (n, mean, standard error, standard deviation, median, 25th percentile, 75th percentile, minimum and maximum) of results at study screening and study Wk 9 visit, as well as the change and percent change from Baseline, will be presented in summary tables; for the categorical responses to overall interpretation, the worst results and the associated findings at scheduled visit will be summarized by counts and percentages. All the ECG data collected will be listed.

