#### **8.5.4. Safety Monitoring for Potassium**

In the event of a potassium measurement  $\geq 5.5$  mmol/L at any time during the study (Treatment or Post-Treatment Period), the initial measurement(s) should be confirmed. If the initial potassium measurement is confirmed to be  $\geq 5.5$  mmol/L study drug is to be held. An ECG evaluation should be performed if the value is confirmed and signs of hyperkalemia should be assessed (delayed conduction, heart block, arrhythmias). If new signs consistent with hyperkalemia are present, proceed to stopping rules. The subject will start oral hydration with 1-liter fluids not containing potassium to induce diuresis. Measure potassium frequently until documented to be  $< 5.5$  mmol/L. Dosing with study drug may continue after a confirmed potassium measurement  $< 5.5$  mmol/L with Investigator and Sponsor Medical Monitor or designee consultation.

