#### 8.6.4. Stopping Rule for Potassium

In the event of confirmed potassium of  $\geq 6.0$  mmol/L or  $\geq 5.5$  mmol/L *with* new ECG changes consistent with hyperkalemia at any time during the study, dosing of a subject with Study Drug will be stopped permanently. The subject should stop any medications (e.g., ACE/ARB) or high K+ diet/supplements affecting potassium levels. Measure potassium frequently until documented to be  $< 5.5$  mmol/L. If there are ECG changes consistent with hyperkalemia or muscle weakness the subject should be admitted to the hospital. The Investigator may consider obtaining a nephrology consultation with consideration for dialysis to treat hyperkalemia. Additional consultation of the Investigator with the Sponsor Medical Monitor may be considered to individualize treatment plan.

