**Appendix A Schedule of Procedures (Continued)**

	Screen	Treatment Period (8 Weeks)									Post-Treatment Period (13 Weeks)					
Study Week		Wk1	Wk2	Wk3	Wk4	Wk5	Wk6	Wk7	Wk8	Wk9	Wk10	Wk12	Wk14	Wk18	Wk21	
Study Day	D-28 to D-1	D1	D3	D8	D15	D22	D29	D36	D43	D50	Treatment Early Term  / D57	D64	D78	D92	D120	PT Early Term  / D141
Visit Window (Days)	NA	NA	+2	± 2	± 2	± 2	± 2	± 2	± 2	± 2	± 2	± 2	± 2	± 5	± 5	± 5
Scheduled Visit #	1	2	3	4	5	6	7	8	9	10	11	12	13	14	15	16
AEs	X	X	X	X	X	X	X	X	X	X	X	X	X	X	X	X
Concomitant Medications	X	X	X	X	X	X	X	X	X	X	X	X	X	X	X	X
PK Blood Sampling 		X a	X a	X a	X a	X a	X a	X a	X a	X a	X	X	X	X	X	X
Immunogenicity Testing		X a									X					X
Archived Serum Sample 		X		X			X			X	X			X		X

Note: D = Day  
W = Week

- 1 Full physical exam to be given at Screening and abbreviated physical exam to be given during Treatment and Post-Treatment Period as indicated to assess changes from Screening
- 2 Vital Signs (clinic): Blood Pressure (SBP/DPB; sitting), Orthostatic assessment (supine and standing, required at Screening), HR, RR, T. Vital sign assessments will be reviewed by the study doctor at each visit prior to dosing.
- 3 Women who are not surgically sterile, as confirmation of menopause
- 4 Women who are not surgically sterile. Serum test to be done
- 5 Refer to [Appendix C](#) for PK sampling schedule
- 6 Stored at -80 °C for follow-up exploration of laboratory findings and/or AEs (e.g., measurement of cytokine and/or chemokine levels, measurement of additional markers of kidney function, measurement of antibodies, etc.) in this or subsequent clinical studies of ISIS 757456
- 7 If the platelet value, serum creatinine or liver enzyme tests are uninterpretable (e.g., due to clumping, hemolysis or quantity not sufficient) a repeat blood specimen; should be re-drawn as soon as possible (ideally within 7 days) and not meet a stopping rule prior to next dose. Due to time constraints, a local lab draw is recommended if a repeat blood specimen is necessary to continue dosing at any time after Study Day 1 to Study Day 8.
- 8 Height at Screening only
- 9 Subjects who terminate treatment or post-treatment early from the study should be encouraged to participate in an early termination visit, at which time the Study D57 or Study D141 assessments should be conducted, respectively

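### The by-arm ECG interpretation table takes only scheduled-visit tracings, so ECGs done for confirmed high potassium and labelled unscheduled reach only the listing

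*Combined protocol and SAP*

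**What the plan says.** Protocol 1.2.4 names abnormal ECG findings as part of the safety endpoint, and Protocol 10.6.2 has ECG measures tabulated by treatment group without limiting them to scheduled visits. SAP 3.7.5 sets the detail. Continuous ECG variables are summarized at Screening and Week 9, and "for the categorical responses to overall interpretation, the worst results and the associated findings at scheduled visit will be summarized by counts and percentages". The same section puts every ECG collected into a listing.

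The general rule in SAP 3.2.1 (Analytical visits) points the same way: results labelled unscheduled "will not be included in the by-visit summary tables and figures except for determining baseline and the analysis of confirmed ALT/AST category".

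Some ECGs are not on the schedule. Protocol 8.5.4 covers potassium of 5.5 mmol/L or more in either period: "An ECG evaluation should be performed if the value is confirmed and signs of hyperkalemia should be assessed (delayed conduction, heart block, arrhythmias"). It continues: "If new signs consistent with hyperkalemia are present, proceed to stopping rules". Confirmation needs a fresh specimen. Protocol 8.5 says of these: "All new specimen collections should take place as soon as possible (ideally within 3 days of the initial collection"). Under Protocol 8.6.4, treatment also ends for potassium of 5.5 mmol/L or more with "new ECG changes consistent with hyperkalemia at any time during the study, dosing of a subject with Study Drug will be stopped permanently".

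**The concern.** An ECG done because potassium is confirmed high is more likely than a routine tracing to show a conduction or rhythm problem. Hyperkalemia is also a plausible risk here. Protocol 2.2 names it as a complication of combined RAAS blockade, every subject takes an ACE inhibitor or an ARB, and the study drug acts upstream on the same pathway.

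As written, the table can leave out those tracings. Its worst-result rule also has little to choose from, because the schedule supplies only one post-dose ECG visit per subject. At stake is whether the by-arm ECG display describes the abnormal findings seen in the study or only those at Day 57 or early termination. No primary or secondary efficacy result depends on it.

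**Working it through.** The plan states no figure to reproduce. The check counts marks in Appendix A and then sets the rules side by side.

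**Scheduled ECGs.** The ECG row has two marks: Screening, and Day 57/treatment early termination. Scheduled post-dose ECG visits = 1.

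**Scheduled potassium draws.** Potassium is in the chemistry panel (Appendix B). Chemistry marks after Day 1 are:
- before Day 57: Days 8, 15, 22, 29, 36, 43, 50 = 7
- on Day 57 = 1
- after Day 57: Days 64, 78, 92, 120, 141 = 5

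Total = 7 + 1 + 5 = 13. Shares: 7/13 = 54%, 1/13 = 8%, 5/13 = 38%. A high Day 57 value confirmed on a later day leads to an ECG after Day 57, so up to 5 + 1 = 6 of 13 (46%) can do so.

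**Which ECGs the table takes.** SAP 3.7.5 restricts the interpretation table to scheduled visits. The word worst could mean worst across visits or worst of several tracings at one visit; either reading leaves unscheduled tracings out. The SAP 3.2.1 exceptions are baseline and confirmed ALT/AST only. Nothing in either rule changes at Day 57.

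**Would a for-cause ECG be labelled unscheduled?** Take a retest 3 days after the draw. This is an assumption, since 3 days is the outer end of the ideal interval.
- Days 8 to 50: visit windows are ±2 days and visits are 7 days apart. Draw + 3 is past the draw's own window (draw + 2) and before the next one (draw + 5).
- Day 57 + 3 = 60, own window 55–59: outside
- Day 64 + 3 = 67, own window 62–66: outside
- Day 78 + 3 = 81, own window 76–80: outside
- Day 92 + 3 = 95, own window 87–97: inside
- Day 120 + 3 = 123, own window 115–125: inside
- Day 141 + 3 = 144, own window 136–146: inside

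A retest after 1 or 2 days would fall inside the triggering visit's window in every case, if that visit took place on its nominal day. SAP 3.2.1 assigns results by the visit label in the data. Dates therefore do not settle which for-cause ECGs carry a scheduled label. The gap applies to those labelled unscheduled.

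**Subjects who stop treatment.** The Protocol Synopsis (Study Visit Schedule and Procedures) has subjects who discontinue carry out the Day 57 procedures at discontinuation. These include an ECG, and that ECG is tabulated. Appendix A, footnote 9 is softer: "Subjects who terminate treatment or post-treatment early from the study should be encouraged to participate in an early termination visit". Protocol 8.8 gives ideally 2 weeks from the last dose. The tabulated tracing may therefore be close to the event or may follow correction of potassium; the documents allow both.

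**The case against.** The strongest case for leaving the plan alone is that tabulating scheduled ECGs and listing the rest is a deliberate and common rule. It keeps the number of looks comparable between arms. With about 30 subjects randomized 2:1, roughly 20 and 10, a listing can be read in full. Screening excludes potassium above 4.9 mmol/L, and potassium-sparing diuretics and other drugs that may cause hyperkalemia are barred, so triggers may be few.

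The important events also have other routes into by-arm output. Protocol 8.6.4 says: "If there are ECG changes consistent with hyperkalemia or muscle weakness the subject should be admitted to the hospital". Admission beyond 24 hours is a seriousness criterion (Protocol 9.3.3). Arrhythmia due to hyperkalemia is a named adverse event example (Protocol 9.5.1). SAP 3.7.2 tabulates all, serious and discontinuation-related TEAEs, and its TEAE rule sets no post-treatment cut-off. Potassium itself is summarized by arm and visit.

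Most of this stands, and it is why the point is minor. It does not close the gap. An ECG abnormality that the investigator does not report as an adverse event, or groups under one diagnosis such as hyperkalemia as Protocol 9.4 encourages, has no by-arm display of its own.

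A reader might infer two stronger statements. One is that the loss lies mainly after Day 57, because no scheduled ECG follows. The documents do not support this: the exclusion is the same on both sides, and 7 of the 13 draws come before Day 57, when no ECG is scheduled either. The other is that every late for-cause ECG would be unscheduled. The window check above and assignment by data label leave that open.

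**Conclusion.** The point holds, at low impact. The by-arm interpretation table draws on one scheduled post-dose ECG visit, while 13 scheduled potassium draws, spread over both study periods, can each prompt a further ECG. Those labelled unscheduled appear only in the listing.

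This rests on reading the scheduled-visit limit in SAP 3.7.5 literally and on for-cause tracings actually receiving an unscheduled label. The documents give no rate of confirmed hyperkalemia, so no expected number of omitted ECGs is claimed. Nor can one infer that hyperkalemic ECG changes would disappear from by-arm reporting, or that a subject stopped for hyperkalemia has no tabulated ECG. The adverse event tables and the Day 57 procedures at discontinuation cover most of that. What remains is ECG abnormality on a named safety endpoint that is never coded as its own adverse event.

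**What to change.** Keep the scheduled Week 9 summary in SAP 3.7.5 unchanged. Add one row by arm on the Safety Set: each subject's worst post-baseline overall interpretation from all ECGs, scheduled and unscheduled. Add this row to the exceptions in SAP 3.2.1, beside confirmed ALT/AST, which is already a precedent for using unscheduled safety results. Footnote the number of unscheduled ECGs per arm.

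The cost is two wording edits and one table row with its footnote, from data already collected and listed; no visit or test is added. The downside is that for-cause ECGs can give one arm more chances of an abnormal reading. The footnote and the retained scheduled summary show that imbalance but do not remove it.
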